9 HOLE PEG TEST

Directions for Participant:

"You are going to take the pegs from the container, one by one, and place them into the holes on the board, as quickly as possible. You must then remove the pegs from the holes, one by one, and replace them back in the container. You may use the hand not being tested to hold the edge of the container to provide stability. You will have 120 seconds to complete this task. Do you have any questions?"

Notes t	to tester:			
	Test should be administered to both hands, starting with the unaffected hand			
	The board should be placed at the participant's mid	dline		
	Participant is allowed up to 120 seconds to comple	ete the task		
	Document the number of pegs placed and the total	time per hand		
	If the participant cannot complete the activity, num documented as 0 and total time should be documented as 0.	nber of pegs placed should be nted as 120+		
	UNAFFECTED HAND	AFFECTED HAND		
Numbe	per of pegs placed: Nu	mber of pegs placed:		
Total T	Time (min:sec): Tot	al Time (min:sec):		

MONTREAL COGNITIVE ASSESSMENT (MOCA)

NAME: Education: Sex:

Date of birth: DATE:

VISUOSPATIAL / EXE	CUTIVE		Сору		(Ten past eleven)	POINTS
Œ			cube	(3 points)		
End	A		+			
5		 				
(1)	(B) (2)					
Begin						
(D) (4) (3)					
	[]		[]	[]		/5
NAMING				Contour N	umbers Hands	
NAMING	F. Elizab	~	~			
	Enligh		1.10		, ,	
	-(mg		Will A	· 3		
			(e))	?\\	
6	1	lab la las	page 1			
	[]		[]		[]	/3
MEMORY repeat them. Do 2 trials, e	lead list of words, subject		FACE VEL	VET CHURCH	DAISY RED	No
Do a recall after 5 minutes		1st trial 2nd trial				points
ATTENTION R	lead list of digits (1 digit/		o repeat them in the	ne forward order	[]21854	
			o repeat them in th	ne backward order	[] 742	/2
Read list of letters. The su	bject must tap with his h			KLBAFAKDEA	A A J A M O F A A B	/1
Serial 7 subtraction starti					/3	
LANGUAGE R	4 or 5 correct subtractions: 3 pts , 2 or 3 correct: 2 pts , 1 correct: 1 pt , 0 correct: 0 pt Repeat: I only know that John is the one to help today. []					
Floor on / Name on	The cat always hid under the couch when dogs were in the room. []					/2
	me maximum number of words in one minute that begin with the letter F					/1 /2
DELAYED RECALL	Has to recall words	FACE VELVE		DAISY RED	Points for	/2
DELATED RECALL	WITH NO CUE	[] []	[]	[] []	UNCUED recall only	
Optional —	Category cue Multiple choice cue				_	
ORIENTATION	·	Month [] Y	ear []D	l  	[] City	/6
© Z.Nasreddine MD		www.mocatest.		mal ≥ 26 / 30 TOT	,	/30

Participant ID:	
Date:	
Testing Session:	

Affected Hand (circle one): Left Right

Modified ladder method: Touch-test sensory evaluator

Product Number	Evaluator Size	Target Force in grams	Representation	Palmar Hand & Dorsal Foot Thresholds	Plantar Thresholds
NC12775-01	1.65	0.1818			
NC12775-02	2.36	0.02	Green	Normal	
NC12775-03	2.44	0.04	Green	NOTHAL	Normal
NC12775-04	2.83	0.07			
NC12775-05	3.22	0.16	Blue	Diminished	
NC12775-06	3.61	0.4		Light Touch	
NC12775-07	3.84	0.6			
NC12775-08	4.08	1	Purple		Diminished
NC12775-09	4.17	1.1			Light Touch
NC12775-10	4.31	2			
NC12775-11	4.56	4			Diminished
NC12775-12	4.71	6			Protective Sensation
NC12775-13	4.93	8			Sensauon
NC12775-14	5.07	10		Loss of	
NC12775-15	5.18	15	Red	Pr	Loss of
NC12775-16	5.46	26			Protective
NC12775-17	5.88	60			Sensation
NC12775-18	6.10	100			
NC12775-19	6.45	180			
NC12775-20	6.65	300			
				l .	

[figure not shown]
Start at 4.31 work up or down in sequence, record lowest level detected with three consecutive accurate responses:

Index finger R:	Index finger L:
-----------------	-----------------

BRIEF KINESTHESIA TEST

Motor Qualifier: Participants must be able to touch and hold for 3 seconds the center circle using vision to qualify to perform this measure. If unable, test only unaffected side.

Participant #:	Date:	
Testing Session:		
Affected Side (circle one): Left	Right	

Demographic Information
Subject #:
Current date:
Date of Stroke: (stroke that resulted in hemiparesis if more than 1 stroke)
Birthdate:
Handedness prior to stroke: Right Left Ambidextrous
More affected side: Right Left
Etiology: Ischemic Hemorrhagic Unknown
Race/ethnicity:

OSU RESEARCH STAFF ONLY BELOW THIS LINE

Caregiver

Parent(s)

Rural: Yes No

SES:

Gender:

Spouse

Male

Female

Who lives with you? (circle all that apply): Child(ren)

Years Education (e.g., H.S.=12; college degree = 16): _____

Other

Adult Child(ren)

Therapist Observations to be collected on LAST day of treatment:

Involvement of Caregiver (check one):
0 – Limited caregiver support (caregiver not present, did not engage in treatment, or doesn't help much at home)
1 – Supportive caregiver (s) – assists when appropriate and encourages independence when possible
2 – Enabling caregiver(s) – assists too frequently
Level of Emotional Support in Family Environment (check one):
0 – little emotional support or frequent interpersonal conflict
1 – more supportive than not

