Relatively relaxed enrollment criteria will be employed to include a representative sample of patients with upper extremity motor impairment. Patients who have experienced a stroke (of any etiology) resulting in hemiparesis at least six months prior, have preserved ability to comprehend and participate in basic elements of the therapy, who have corrected vision of at least 20/70 (individuals with low vision would have difficulty participating in the gaming intervention), who are not currently participating in other experimental upper extremity trials, who are not currently engaged in other outpatient rehabilitation for their upper extremity, and who have not received Botox within the last 3 months (confound) will be eligible to participate. Eligible participants will receive an in-person screening to ensure their ability to safely engage in rehabilitation. Patients deemed too frail to undergo intensive rehabilitation or those with serious, uncontrolled medical problems will be excluded (e.g., debilitating pain). The recruited sample will represent approximately 50% of individuals with hemiparesis. Participants will be stratified by severity of impairment (see table below) and separately randomized to reduce potential baseline inequality between groups.

Severity of	Shoulder	Elbow	Wrist	Fingers	Thumb
Impairment					
Mild-	Flexion ≥45° and	Extension ≥20°	Extension ≥20°	Extension of all	Extension or
moderate	Abduction ≥45°	from a 90° flexed	from fully flexed	MCP and (PIP or	abduction of
		starting position	starting position	DIP) joints ≥10°	thumb ≥10°
Moderate	Flexion ≥45° and	Extension ≥20°	Extension ≥10°	Extension MCP	Extension or

Abduction ≥45°	from a 90° flexed	from fully flexed	and (PIP or DIP)	abduction of
	starting position	starting position	joints of at least 2	thumb ≥10°
			fingers ≥10°	

Measurement/Instrumentation

Primary measures:

- Motor Activity Log
- Wolf Motor Function Test

Secondary measures:

- bilateral activity monitors (accelerometers)
- Patient Health Questionnaire (PHQ-9)
- Touch Test Monofilaments
- Neuro-QOL
- 9-Hole Peg Test
- Brief Kinesthesia Test
- Kinematic Analysis (performed on skeletal Kinect data collected during game play)
- Montreal Cognitive Assessment (MoCA)

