This criterion is most useful for identifying which participants with higher motor functioning are eligible to participate. There is no maximum level of motor ability for the study, but participants must exhibit non-use of the weaker arm (score less than 2.5 on the QOM portion of the MAL). When non-use is obvious and motor impairment is pronounced, you need not administer MAL.

- MAL QOM less than 2.5
- ✓ Does the participant meet these criteria? Y N

VI. Pain

Potential participants will be given the option to self-exclude if they have pain that would be significantly aggravated by participation in the protocol. Consider missed days in carrying out everyday tasks due to pain and excessive discomfort.

VII. Anti-Spasticity Agents:

Participants receiving Botox injections may be scheduled after 12 weeks from when the Botox injection was administered. If the participant is using other antispasticity agents such as oral Baclofen, then that information will be noted but will not used as inclusion / exclusion criteria.

• More than 12 weeks from last Botox injection at start of trial

Are you currently using Baclofen, Dantrium or any other anti-spasticity agen If so, which one?	its? Y	N	
If botox, date of last injection?			
✓ Does the participant meet these criteria? Y N			
VIII. Administer 9-hole peg test			
If participant qualifies, see whether he/she falls in higher or lower functioning growill be based on the participant's ability to complete placement of any number of peg test within the allotted time (120 seconds).			
Higher group: can place ANY number of pegs (1-9) Lower group: cannot place any pegs			
✓ Which group is the participant assigned to?			
IX: Additional Questions			
	(circle one)		
Are you able to maintain standing balance for 2 minutes; using UE for support if needed without the assistance of another person?	Y	N	
Are you able to independently and safely transfer to/from the toilet and manage clothing/hygiene?	Y	N	
Are you able to independently stand from a sitting position?	Y	N	
Do you plan to use a device during the trial (e.g., Saebo)?	Y	N	
X: Summary and Planned Follow-up:			
XI: If enrolled			
Randomization Group?			
Date of Pretest:			
Date of Post-test:			
Date of 6-month follow-up:			

Treatment materials – CI therapy

Checklist

Note: Bolded items are separate sheets within the treatment packet to be completed

Prior to Treatment (after pre-test)

- 1. Provide the activity monitors to participants and demonstrate use.

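### The 9-Hole Peg Test note, on its natural reading, scores every non-finisher as 0 pegs and hides partial gains; separately, severity groups are defined in two unreconciled ways

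*Combined protocol and SAP*

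**What the plan says.** **Scoring.** The 9-Hole Peg Test is listed as a secondary measure under Measurement/Instrumentation. On its form, the participant places the pegs one by one, and then: "You must then remove the pegs from the holes, one by one, and replace them back in the container". The limit follows: "You will have 120 seconds to complete this task". The notes to the tester repeat the 120-second allowance and instruct: "Document the number of pegs placed and the total" time for each hand. The last note reads, in the extracted text, "If the participant cannot complete the activity, num documented as 0 and total time should be", with the displaced remainder "nber of pegs placed should be nted as 120" and a plus sign. This is two printed lines interleaved by text extraction, not a fault in the protocol. Rejoined, the note says that when the activity cannot be completed, the number of pegs is entered as 0 and the total time as 120+.

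**Severity groups.** Sample & Inclusion/Exclusion Criteria says: "Participants will be stratified by severity of impairment (see table below) and separately randomized to reduce potential baseline inequality between groups". Its table has two rows, mild-moderate and moderate, defined by active range of motion; pegs are not mentioned. Item VIII of the RCT In-Person Participant Screening Form instead sorts qualifying participants by the peg test within 120 seconds: "Higher group: can place ANY number of pegs (1-9"; the lower group can place none. It then asks which group the participant is assigned to.

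**The concern.** A count of pegs is useful in this population because many levels of ability lie between placing none and finishing the whole task. Entry requires only about 10° of wrist, thumb and two-finger extension plus picking up and releasing a washcloth, and the screening form has a category for people who place no peg. So the trial expects some participants near the bottom of the scale. If every unfinished test is entered as 0 pegs and 120+, neither field separates these participants from one another, and improvement short of completion cannot be seen in either arm of a comparison.

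If instead the note is meant only for people who place no peg, the form does not say so. Testing is done at several sites, and two assessors could enter 5 and 0 for the same performance.

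The second matter concerns the design. A reader cannot tell from the documents whether randomisation was stratified by range of motion or by the peg test. An analysis by severity, or a check of balance within strata, needs that answer.

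**Working it through.** The plan gives no numerical figure on this point to reproduce, so the check is an enumeration.

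**Inputs** (all from the peg-test form and screening item VIII): nine pegs; placement followed by removal; a limit of 120 s; a rule of 0 pegs and 120+ when the activity cannot be completed; higher group = 1–9 pegs, lower group = 0.

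**Possible results.** Ten unfinished results (0, 1, …, 9 pegs placed, removal not finished in time) plus one finished result: 10 + 1 = 11.

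**Two readings of the note.** A: not finished in 120 s. B: no peg placed.

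| True result | Recorded under A | Recorded under B |
|---|---|---|
| 0 placed | 0, 120+ | 0, 120+ |
| k placed, k = 1 to 8 | 0, 120+ | k, time rule not stated |
| 9 placed, not all removed | 0, 120+ | 9, time rule not stated |
| Finished | 9, actual time | 9, actual time |

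**Range of recorded counts.** Under A, only 0 and 9. Under B, 0 to 9.

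**Results with at least one peg placed but recorded as 0.** Under A, 8 (k = 1 to 8) + 1 (9 placed, not all removed) = 9 of 11. Under B, 0 of 11. These are kinds of result, not proportions of participants.

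**Effect on change scores under A.**
- 2 pegs, then 8: true change 8 − 2 = +6; recorded 0 − 0 = 0.
- 0 pegs, then 8: true change +8; recorded 0, with time 120+ at both visits.
- 8 pegs, then finished: true change 9 − 8 = +1; recorded 9 − 0 = +9.

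**Which reading is more natural?** For A: the form ties completing the task to the 120-second limit, and 120+ is the code of a time-out. For B: the note just before asks for the number placed, which would add nothing to the time field if it could only be 0 or 9; and item VIII recognises partial counts. A is closer to the words; B is possible.

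**After the fix below.** Counts run 0 to 9, and no result with a peg placed is recorded as 0.

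**The two severity definitions side by side.** The table's two rows share the shoulder, elbow and thumb thresholds. They differ at the wrist (≥20° against ≥10°) and the fingers (all fingers against at least two). The listed criteria on the screening form ask only whether the lower thresholds are met: wrist 10° or more, at least two additional digits. The table's strata therefore cannot be read off those criteria. The only severity grouping the form records is the peg group, and no passage maps it to the table.

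**The case against.** The strongest reply is that the note does not mention running out of time. It says the participant cannot complete the activity, which can mean being unable to do it at all. Read that way it agrees with the preceding note, the separate count field for each hand and item VIII, and no information is lost. This stands as a possible reading, so the loss of partial gains is conditional. It does not clear the form: the key term is undefined, and this reading leaves the time entry for partial placers unstated.

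A reader might also infer that the scoring note moves people from the higher to the lower group. The documents do not support this. Item VIII records the group on the screening form itself, and nothing derives it from the count on the test form. The mismatch would arise only if someone rebuilt the group from the pre-test count under reading A.

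A reader might further infer that participants were randomised in the wrong strata. That is also unsupported. The screening form asks for the randomisation group in a later item, but never calls the peg group the randomisation stratum.

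Finally, the reach is limited. The Data Analysis paragraph specifies models for the primary outcomes only and includes no stratum term. It states no analysis for the peg test, which is also absent from the outcome schedule table, although the text above that table covers the measures in general. Aim 4b names initial motor ability as a moderator without tying it to either grouping. All of this stands.

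**Conclusion.** The point holds in two limited parts.

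1. On its most natural reading, the tester note collapses the peg count to 0 or 9 and conflicts with the instruction to record the number placed. The loss for an individual can be large (a gain of 6 pegs recorded as 0), but the documents do not give the share of participants who place some pegs without finishing, so the effect on an arm comparison cannot be sized. It would be wrong to say that the measure sits at a floor for most participants. On the other reading the loss does not arise, and what remains is an undefined term open to inconsistent scoring. One secondary measure is affected either way; the primary outcomes are untouched by this note.

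2. Severity is defined by range of motion in the protocol body and by the peg test in screening item VIII, with no link between them. This is a gap to be reconciled, not evidence that randomisation went wrong.

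The conclusion rests on the rejoined wording of the note, which is a reconstruction, though the fragments fit in only one sensible way.

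**What to change.** **Peg-test form.** Replace the last tester note with a rule that needs no interpretation: enter the number of pegs actually placed by 120 seconds (0 to 9); enter 0 only when none was placed; for anyone who has not finished placing and removing by then, enter 120+ and treat total time as censored at 120 seconds. Analyse the count and the censored time as they stand. A rate such as pegs per second is not available, because the form has one total time that includes removal and no separate placement time.

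**Severity.** In Sample & Inclusion/Exclusion Criteria and in item VIII, state the single variable that fed the randomisation and how the other grouping, if kept, relates to it. Use the value recorded at randomisation as the stratum in any analysis by severity, and do not re-derive it from the pre-test form.

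**Cost.** One sentence on a form that already has the count field, a reminder to assessors, and a sentence or two to align the severity definitions. The one real loss is retrospective: forms already scored 0 under the present note may be recoverable only from video of the testing session, where it exists.
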